32 The NICHD (National Institute of Child Health and Human Development) Study of Early Child Care and Youth Development (SECCYD), was based on 1,261 children recruited at birth and assessed at 15, 24, 36, and 54 months. The study measured childcare quality in two ways: structural or regulable features of childcare (such as adult-child ratio, group size, caregiver's education level) and process features (such as showing a positive attitude, having positive physical contact, responding to vocalisations, asking questions, praising, encouraging, teaching, telling, singing and eliminating negative interactions). It found that both structural and process features of childcare were 'modestly to moderately predictive' of child outcomes (NICHD Early Child Care Research Network, 2006a:99) but also found that 'only a small percentage of children received a lot of positive caregiving' (NICHD Early Child Care Research Network, 2006b:11). The policy implications of these findings directly support the NEYAI logic model: 'Our results provide support for programs designed to improve child-care quality. These include policies that invest funds in child-care teacher training and professional development, offer incentives to programs to provide quality care, support regulations and

other fields, such as counselling and psychotherapy, there is evidence that front-line staff characteristics, and the therapeutic relationship formed with clients, has an impact on outcomes³³. Across these different studies, an overarching finding is the strong association between the quality of adult-child interactions and the quality of child outcomes³⁴, and this knowledge is reflected in the importance given to ‘interactions’ in both the National Framework for Early Childhood Education (Síolta³⁵) and the Early Childhood Curriculum Framework (Aistear³⁶).

inspections, offer vouchers so that parents can afford higher quality care programs, and fund programs such as Head Start and prekindergarten that allow access to high-quality care for children from low income families. Because high-quality care for infants and toddlers is often unavailable, it is especially important to focus efforts on improving the quality for children younger than three years of age In addition, our results provide support for policies that reduce the amount of time children spend in child care. . . . the findings from the NICHD SECCYD also support policy initiatives that promote growth-facilitating parenting, including home-visiting programs already demonstrated to be effective in this regard’ (Ibid:114).

[figure not shown]
33 The therapeutic relationship is seen by many commentators as ‘the sine qua non of successful therapy’ (Sprenkle, Blow and Dickey, 1999:334). It has been suggested that many of the qualities of effective therapist-client relationships – emotionally warm, available, attentive, responsive, sensitive, attuned, consistent and interested - are in fact generic to many relationships both in work and family (Howe, 1999:99). The writings of Carl Rogers laid particular stress on the helping relationship by emphasising the need to show clients – and be experienced by clients as showing – unconditional positive regard, accurate empathic understanding, and openness to creative solutions (Rogers, 1957). One review of the literature, based on the findings of over 1,000 studies, recommended three ways to improve the therapeutic relationship: (1) accommodate the client’s motivational level and state of readiness for change; (2) accommodate the client’s goals for therapy; and (3) accommodate the client’s view of the therapeutic relationship (Hubble, Duncan and Miller, 1997:Ch.4; Duncan 2010). These considerations, while specific to the therapeutic context, have more general applicability to all caring relationships.

34 For a review, see French, 2011.

35 Standard 5 (of 16) states: ‘Fostering constructive interactions (child/child, child/adult and adult/adult) requires explicit policies, procedures and practice that emphasise the value of process and are based on mutual respect, equal partnership and sensitivity.’ (Department of Education and Skills, 2010a:39).

36 One of the four guidelines for good practice is ‘learning and developing through interactions’. It states: ‘Relationships are at the very heart of early learning and development. Through their early interactions babies learn to feel secure, to communicate, and to enjoy being with people. As they grow and develop, toddlers and young children love to play, to chat, to watch, and to be with others. Children build relationships, communicate, express love and affection, play together, learn, and have their needs met through contact with others. These guidelines identify a range of interaction strategies and methods which the adult can use to enhance children’s learning and development.’ (National Council for Curriculum and Assessment, 2009:27).

Figure 2 Influences on the Well-Being of Parents and Children

Note: The relationship between each independent variable and the two dependent variables (parent well-being, child well-being) is expressed as a standardised coefficient and reflects the relative weight of influence of each independent variable on the dependent variables. Thus, for example, the two largest influences on parent well-being are positive affect (.43) and socio-economic status (.36) while the two largest influences on child well-being are the parent's relationship to the child (.58) and the parent's well-being (.46). Source: Pratschke, McKeown and Haase, 2011.

In the area of project capacity more generally, the evaluation of Sure Start found that child and parent outcomes were better in projects which were more proficient at implementing the 18 guiding principles of the programme³⁷. Although the 'detected relationships are not strong'³⁸, the evaluation drew attention to 'empowerment' as an aspect of implementation that merited attention; this aspect of capacity was defined as 'the extent to which procedures are in place that actually increase parent and staff participation and collaboration in decision-making and programme activities. The programme characteristics that go with empowerment include community groups and parents being involved in the planning and delivery of services; parent representation; staff training opportunities; clear exit strategies for users; services to include self-help groups; evidence that staff and users constitute a learning community; and evidence of mutual respect for all parties.'³⁹

Finally, inter-agency cooperation is seen as an important aspect of capacity in the NEYAI but quite challenging to assess from an evaluation perspective. Possibly because of this, there are few well-designed studies which show that interagency working has substantial measurable impacts on services users⁴⁰; although there are studies which show positive outcomes for professionals and

37 This was based on a random sample of 150 of the first 260 Sure Start Programmes in England and a random sample of 12,575 nine-month olds and 3,927 three year olds. The 18 guiding principles of Sure Start Local Programmes (SSLPs) are: (1) SSLP has a well-articulated vision that is relevant to the community; (2) SSLP Partnership Board includes a balanced representation of local organizations, local education authority, social services, local NHS, voluntary and community organizations, and local parents; (3) The Partnership is functional; (4) SSLP has an intention to empower users and service providers; (5) Communication systems reflect and respect the characteristics and languages of the host communities; (6) SSLP has effective leadership/management; (7) Multi-agency teamwork is established in the SSLP; (8) There are clear pathways for users to follow in accessing specialist services; (9) Staff turnover is low; (10) SSLP takes account of and acts upon evaluation findings; (11) SSLP has strategies for identification of users; (12) SSLP is showing a realistic and improving reach of children in the area; (13) SSLP is aware of reach and has strategies to improve/sustain use of services over time; (14) Service delivery reflects the guidance requirements for the provision of core services in support, health, and play & childcare; (15) SSLP service delivery reflects intention to target children, parents & families and the community; (16) SSLP shows innovative features; (17) Services accommodate the needs and preferences of a wide range of users; (18) Overall, the SSLP has a welcoming and inclusive ethos (National Evaluation of Sure Start Team, 2005b, Appendix 5).

38 Melhuish, Belsky, Anning, Ball, Barnes, Romaniuk, Leyland and the NESS Research Team, 2007:548; see also National Evaluation of Sure Start Team, 2005b. This was based on a random sample of 150 of the first 260 Sure Start Programmes in England and a random sample of 12,575 nine-month olds and 3,927 three year olds.

39 'The finding that empowerment is related to two of the eight measures of programme impact upon child and parenting outcomes, in particular two of the five parenting measures (9-month-old maternal acceptance, 36-month-old home learning environment), suggests that strengthening programme activities relevant to empowerment should improve their effectiveness in influencing parenting. Note that empowerment in this study is not a self report measure.' (Melhuish, Belsky, Anning, Ball, Barnes, Romaniuk, Leyland and the NESS Research Team, 2007:59).

40 'For despite much rhetoric about, and investment in, partnership working as the panacea for complex problems, we still know relatively little about the workings of these strategic partnerships and how they actually engage with, and improve, front-line practice and outcomes for service users. ... Indeed, we are in only the early stages of identifying evidence that such partnerships improve outcomes' (Morrison, 2010:313). A meta-analysis of the effectiveness of early years programmes found that 'comprehensive services are neither necessary nor sufficient for large sustained gains' (Barnett, 2011:977). In Ireland, a qualitative study of a five-year inter-agency process found that 'a good inter-agency process alone may not guarantee better outcomes' (McKeown, 2011; 2012).

agencies⁴¹, and also studies which show how the absence of inter-agency working contributes to system failures in protecting children from neglect, abuse or even death⁴². While this does not challenge the value of inter-agency working, or the link between service capacity and outcomes, it draws attention to the need for this evaluation to find out if inter-agency structures translate into changes in how front-line services are delivered and experienced by children and their parents.

Returning to the logic model, the precise way in which the different elements of the model operate in practice, and connect with each other as covariates or causes, cannot be represented in advance of the evaluation. However as a simple framework, it serves to clarify the type of research design which is needed to meet the objectives of the evaluation. It does this by describing the theory behind the programme and identifying the different categories of data that need to be collected in order to test if the programme is achieving its expected outcomes and, if so, how. In other words, the logic model sets out a set of hypotheses which will be tested through a statistical model of how NEYAI actually works, based on the evidence available.

4. Research Design

The overall objective of NEYAI can be stated in relatively simple terms: to improve the capacity of childcare services in order to improve outcomes for children and their parents. Equally, the questions at the heart of this evaluation can also be stated in relatively simple terms:

- (i) Does NEYAI have an impact on children and their parents by comparison with a 'matched' sample of those who have not participated in NEYAI?
- (ii) If NEYAI has an impact, how does this come about, for whom, in which projects, using what type of intervention(s), etc?

Designing a research project in order to answer these questions with robust scientific evidence is not a simple undertaking however. That is why it may be useful to begin by setting out some of the challenges encountered in preparing this research design.

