13 For that reason, the proper use of a logic model requires awareness of its limitations since 'the logic model is a model – not reality. It depicts assumed causal connections not true cause-effect relationships' (Taylor-Powell & Henert, 2008). Limitations of logic modelling include the following: (i) a logic model represents intention, it is not reality; (ii) it focuses on expected outcomes so people may overlook unintended outcomes (positive and negative); (iii) it focuses on positive change – change isn't always positive; (iv) it may simplify the complex nature of causal attribution where many factors influence process and outcomes; (v) it doesn't address whether we are doing the right thing – we may get caught up in creating a logic model and lose track of whether the program is the right thing to do; and (vi) may stifle creativity and spontaneity. (Ibid).

The left-hand side of the logic model depicts the inputs of NEYAI and are constituted by the 11 project interventions. These include both the actual services delivered to children and their parents as well as the training and mentoring of staff to deliver those services. These inputs will vary by type, duration and intensity but will also vary in the manner of their implementation. The context of each project, particularly the focus on children living in disadvantaged areas, can also be regarded as an 'input' in the sense that the uptake and effectiveness of each intervention is likely to be affected by characteristics of the target group and the target area. In this sense, context provides important information about how NEYAI is targeted, who participates, and how it influences outcomes directly and indirectly for parents and children (see Section 6.5 below).

The right-hand side of the logic model depicts the outcomes which are conceptualised as improved well-being for children and their parents. For children, this takes the form of improved physical, emotional, social and cognitive development. For parents, it includes improved individual well-being, both physical and mental, as well as improved parenting and family relationships but may also include an improved sense of social support.

Figure 1 Logic Model of National Early Years Access Initiative

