At the centre of the logic model are the hypothesised pathways by which inputs are transformed into outcomes. The first of these is rooted in the circumstances of children and their parents and may include personal well-being (such as physical and mental health), relationships (with child and their partner), support networks, and neighbourhood quality (such as trust and safety). The second is

changes in project capacity denoted mainly by changes in how staff experience their job and their work; it may also include changes induced by the learning community. The third potential pathway is changes in service capacity such as improved local inter-agency cooperation or the implementation of national policy on early years such as the National Framework for Early Childhood Education (Síolta¹⁴) and Early Childhood Curriculum Framework (Aistear¹⁵).

Given the importance of pathways as active ingredients in how programmes work, it is worth documenting briefly some research evidence in support of the pathways which have been identified in the logic model. Beginning with the behaviour and attitude of parents and children, one study of Early Head Start in the US identified the parent-child relationship as a key pathway to improved outcomes for children¹⁶. Similarly, an evaluation of the Child-Parent-Centres in Chicago identified family and school supports for the child's education as key mediators of improved cognitive outcomes for the child, as well as reductions in child neglect and abuse¹⁷. The first phase of the evaluation of Sure Start in the UK found that, while there were relatively few impacts among children – fewer behaviour problems and greater social competence among the three year-old children of

14 Department of Education and Skills, 2010a.

15 National Council for Curriculum and Assessment, 2009.

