5.2 Comparison Group Sample

The comparison group sample is created in three stages. First, the catchment areas of the treatment group are identified in terms of demographic and socio-economic characteristics. For each NEYAI project, its catchment area is defined as the sum of the catchment areas of each childcare centre participating in the evaluation.

The data used to define these catchment areas is derived from the 2006 Census of Population, based on 'Small Areas' which have a minimum of 65 households and an average of 100 households; as such the data is almost 'street-level' and allows catchment areas to be defined precisely. This data will be expressed in terms of its deprivation score using the Pobal-Haase Index⁷². This data has the advantage that it is immediately available and, more to the point, the only data that allows areas to be defined in this way. The disadvantage is that while it is possible to match treatment and comparison areas in terms of deprivation scores, it is not possible to match them on other family characteristics which may be more relevant to this evaluation such as child and parent well-being, family functioning, neighbourhood and community factors. Nevertheless, the use of deprivation scores is the best available option and there are precedents for drawing comparison groups in this way, a notable example being the Sure Start evaluation⁷³.

Second, having established the level of deprivation in these catchment areas, a set of comparison areas will be identified which are matched as closely as possible to the treatment areas. In each of these comparison areas, childcare centres will be drawn from the Pobal database to match the

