6.2 Parent Questionnaire

The purpose of the Parent Questionnaire is to assess the well-being of each mother across a wide range of domains that are recognised as central to personal well-being and the well-being of children. The Parent Questionnaire will be completed using a face-to-face interview with the mother of the 'focus child', the latter defined as the child attending the childcare centre who has been randomly selected to participate in the evaluation. Each parent will be interviewed in the home, or elsewhere if that is her preference, and at a time that is agreed with the interviewer⁸⁴. The Parent Questionnaire is similar to a questionnaire that has been used in numerous studies by members of the research team⁸⁵ – with the addition of some new instruments, some of them from the GUI – and for that reason, it is considered unnecessary to pilot it.

[figure not shown]
The conceptual framework underpinning the Parent Questionnaire is graphically illustrated in Figure 4. There is a detailed guide to every question in Appendix Four and the actual questionnaire is in a separate document. The conceptual framework informing the Parent Questionnaire has already tested in previous work (see Figure 2 above) and this is being further re-analysed using the GUI⁸⁶ dataset. This framework envisages parental well-being as a latent construct which manifests through the parent's personal and relationship experiences and is itself influenced by the parent's personality traits, socio-economic and neighbourhood characteristics, etc.

84 The decision to interview mothers only is based entirely on practical considerations since interviewing fathers as well as mothers is beyond the resources of the evaluation. However the Parent Questionnaire contains two questions on the father's involvement with the child, based on similar questions used in the GUI, the Sure Start evaluation and the Millennium Cohort Study: 'How often can you count on him if you need him to take care of the child?' and 'Overall how close would you say he is to your child?'

85 McKeown, Haase, Pratschke, Lanigan, Burke, Murphy, and Allen, 2008:23-28; McKeown and Haase, 2007; Haase, McKeown, and Pratschke, 2008; Haase, 2009.

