9.2.3 Examine possible pathways associated with each net impact. Using Structural Equation Modelling, analysis of the combined dataset of treatment and comparison group will estimate if there is a difference in outcomes between the two groups and whether, in turn, this is related to the interventions in any or all of the projects. Only when this has been established, will the analysis examine the association between these interventions and other independent variables, since that is how the pathways suggested in the logic model are tested against the evidence. This will involve taking one outcome measure each for children, parents and staff, and then developing a statistical model to explain the pathways by which that improved outcome came about. We will also build a statistical model which combines all three outcome measures in order to show how the well-being of children, parents and staff are inter-connected. Within these models, relationships between variables are measured by standardised regression coefficients and each coefficient measures the unique influence of each variable on the outcome, controlling for all other variables which affect that outcome. This method of analysis is capable of yielding statistically robust insights into the pathways by which change occurs in outcome variables and is increasingly regarded by researchers and statisticians as the appropriate form of analysis for this type of evaluation.

9.2.4 Describe in more detail the interventions and pathways associated with positive impacts, as identified in the models. This is important because it is unlikely that the statistical models, on their own, will contain an exhaustive account of all factors associated with statistically-significant improvements in outcomes. That is why data on the intervention delivered by each project is important (see Section 6.4 above) as well as data from evaluation of the learning community (see Section 6.7 above). Additional case-study data, collected from projects identified as having a positive impact, may also cast light on questions which cannot be addressed easily or

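### Neighbourhood quality is both a possible pathway and pre-existing context, and Section 9.2.3 can report it as the route of an impact without requiring that it changed

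*Protocol*

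**What the plan says.** The protocol gives neighbourhood more than one role.

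- **Possible pathway.** Section 3 places at the centre of the logic model "the hypothesised pathways by which inputs are transformed into outcomes". Of the three pathways it says: "The first of these is rooted in the circumstances of children and their parents and may include personal well-being". The list that follows includes "relationships (with child and their partner), support networks, and neighbourhood quality (such as trust and safety".
- **Context.** Earlier in Section 3, the setting of each project is called a kind of input, because the "uptake and effectiveness of each intervention is likely to be affected by characteristics of the target group and the target area".
- **Determinant.** Section 6.2 says that parental well-being is influenced by the parent's "personality traits, socio-economic and neighbourhood characteristics".
- **Unmatched factor.** Section 5.2 matches areas on deprivation score and says they cannot be matched on characteristics that may be more relevant, among them "child and parent well-being, family functioning, neighbourhood and community factors".

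The test comes in Section 9.2.3. Once a difference in outcomes between the groups has been established and related to the interventions, the analysis will "examine the association between these interventions and other independent variables". The section says that this is how the logic-model pathways are tested. It does not say that a pathway variable must have changed between baseline and follow-up.

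**The concern.** A pathway in the protocol's sense lies downstream of the programme: inputs act on it, and it acts on outcomes. A context variable lies upstream. In a non-randomised comparison of different areas, both produce the same observation at follow-up: the arms differ on the variable, and the variable is related to the outcome. An association with the intervention cannot separate the two. Only timing can, that is, whether the variable moved differently in the two groups after baseline.

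Neighbourhood is especially exposed. The arms are made of different places, the protocol accepts that those places cannot be matched on it, and none of the core activities in Table 1 (staff training and mentoring, parenting courses, support and outreach to families) is described as acting on the neighbourhood.

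At stake is core question (ii) in Section 4: how an impact comes about. The protocol promises to identify active ingredients for policy and practice. A difference between areas reported as one of them would mislead whoever tries to reproduce the programme.

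**Working it through.** The protocol gives no figure on this point, so there is none to reproduce. The check sets the passages side by side and then illustrates the size.

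**1. Do the stated rules exclude a stable gap as a pathway?**
- Section 4.3 (iii) compares changes between groups, but for outcomes, not for pathway variables.
- Section 9.1.1 relies on statistical control of measured differences, but for identifying the impact. A variable tested as a pathway cannot also be adjusted away unless the plan says which wave plays which role.
- Temporality (Section 4.4) is to be met by the before-and-after design; it is not turned into a condition on the pathway variable.
- Section 4.2 (step 5) and Section 9.2.3 examine pathways only after an outcome effect. This blocks the error when there is no effect, but not when NEYAI works by another route.

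**2. How easily is a pre-existing gap seen at follow-up?** Sample per arm (Section 5): 35 − 5 = 30 per project, and 30 × 11 = 330. Significance level 0.05 (Section 5), two-sided assumed. For a gap of d SD, z = d × √(330/2) = 12.85 d, and power is about Φ(z − 1.96):

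| Gap (assumed) | z | Chance of significance |
|---|---|---|
| 0.1 | 1.28 | 25% |
| 0.2 | 2.57 | 73% |
| 0.3 | 3.85 | 97% |

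**3. How often does this become a reported pathway?** Simulation with 330 per arm. Assumed: a gap of 0.2 or 0.3 SD, identical at both waves and untouched by NEYAI; neighbourhood influence of 0.2 on the outcome; correlation of neighbourhood scores between waves 0.7; outcome measured at both waves; no clustering. An evaluation counts as a false pathway if the outcome change differs between arms, the arm is related to neighbourhood, and neighbourhood is related to the outcome.

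| Real effect by another route | Neighbourhood tested on | False pathway |
|---|---|---|
| 0.2 to 0.3 SD | follow-up level | about 59 to 96% |
| 0.2 to 0.3 SD | follow-up adjusted for baseline | about 14 to 36% |
| 0.2 to 0.3 SD | change from baseline | about 3 to 5% |
| none | follow-up level | about 4% |

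The ends of the first row fit step 2. With a 0.2 gap the neighbourhood leg passes 73% of the time, and 0.59/0.73 = 0.81 is the share that also shows an outcome effect. With a 0.3 gap and the larger effect, nearly all do: 0.96/0.97 = 0.99.

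The false indirect effect itself is small, gap × influence: 0.2 × 0.2 = 0.04 SD to 0.3 × 0.2 = 0.06 SD.

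Baseline adjustment is not enough because one baseline score measures the lasting level of neighbourhood imperfectly. The remaining gap still shows at follow-up. In the change score a stable gap cancels.

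**The case against.** The strongest reply is that the protocol commits itself to much less than a fixed neighbourhood pathway and already has general protections.

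- **The wording is tentative.** Section 3 says the first pathway may include these items; only the second and third pathways are worded as changes. The end of Section 3 leaves open whether elements connect as covariates or causes. This stands: a reader might infer that the protocol claims NEYAI changes neighbourhoods, and it does not. But leaving the role open makes the test in Section 9.2.3 carry the decision, and that test cannot make it.
- **Unmatched is not unadjusted.** Section 5.2 concerns the choice of areas from census data. The Parent Questionnaire measures local problems, neighbourliness and trust (items B1-B3, Appendix Four), is given at baseline and follow-up (Appendix Two), and Sections 4.3, 4.4 and 9.2.3 promise control of measured variables. This stands in part. The promise is general, and adjusting follow-up for baseline still leaves about 14 to 36% in the illustration.
- **Pathways are tested only after an impact.** This stands fully for the case of no effect.
- **Model detail may be in a statistical analysis plan.** It may, and the absence of model terms is not the point. The point is that the protocol states a testing rule, and that rule does not separate the two roles it gives to neighbourhood.

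**Conclusion.** The point holds in a limited form. If a net impact is found, a neighbourhood difference that predates NEYAI could be reported as its route, because Section 9.2.3 asks only for association with the intervention.

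Two stronger readings are not supported. First, a reader might infer that an area difference would routinely be confirmed as a pathway even if NEYAI did nothing. The required outcome difference holds that to about 4%, if it is assessed on outcome change as Sections 4.3 and 9.2.2 indicate. Second, a reader might infer that question (i) is biased as well. A gap equal at both waves cancels when changes are compared, so the net impact is untouched by it.

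The 59 to 96% rests on assumed gaps, influence, wave correlation and effect sizes, none of them in the protocol. A smaller gap lowers it: at 0.1 SD the neighbourhood leg alone is significant in only 25% of evaluations. Clustering was ignored; the planned multi-level modelling would lower the rates but would not remove bias from a systematic area gap. The contrast between testing level and testing change is the firm result. It does assume a stable gap: areas already moving apart would mislead the change test too.

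This is worth correcting before the follow-up analysis. It affects the explanation of an impact, not its existence.

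**What to change.** In Section 9.2.3, state that baseline neighbourhood scores (Parent Questionnaire B1-B3) enter the child and parent pathway models as context covariates. Add that neighbourhood quality is accepted as a pathway only if its change from baseline to follow-up differs between the treatment and comparison groups, and never on follow-up level alone. A cross-reference in Section 3 should say that neighbourhood is context unless this condition is met.

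The cost is a few sentences. No new data are needed, since the items are planned at both waves. The downside is some loss of power to detect a genuine neighbourhood pathway, because a change score carries the measurement error of two occasions.
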